## **10.8 Randomization**

Randomization will be performed by a computerized random generator (Microsoft.NET Random Constructor (Int 32)) in a 1:1 allocation ratio. The random generator is integrated in the dispatcher's software and there is no possibility for a dispatcher to see or guess randomization results before randomizing, therefore allocation concealment is preserved before randomization. For implementation the random generator is programmed so one dispatcher can only randomize a specific call one time. The computerized random generator is implemented by SOS-alarm into their software "Cord-comp".

## 11. Interim analysis and data monitoring committee

The trial will be monitored by an independent Data Safety Monitoring Committee (DSMC) that will receive unblinded summaries of data at the two interim analyses scheduled at 750 and 1500 patients. The DSMC will have mandate to evaluate specific safety concerns), as well as efficacy, with the option to either declare sufficient difference in the primary outcome variable, or to recommend that the study is continued until 3260 patients have been enrolled. Early stopping for efficacy reasons will only be considered if primary outcome differences are seen between the groups according to the Peto-Haybittle rule with a p-value  $\leq 0,001$ . The DSMC will be able to request unblinding of data if they find it necessary. The DSMC can initiate analysis at any time they request.

A Interim analysis was performed by an independent data monitoring committee in early 2022, reviewing all data including 30-day survival, after a total of 1250 patients (out of which 696 patients were included in the main PP1 population). The recommendation by the data monitoring committee was to continue the trial without modification.

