## 8. Data collection

### From the dispatch organization (SOS-Alarm AB) the following variables will be collected:

Time of incoming call, time of dispatch of EMS, time of dispatch of first responders when applicable, time for screening for inclusion, time of randomization and time of arrival of EMS and first responders. Event times are automatically generated and stored in the dispatch organization's computer system. The randomized assignment for each call is stored in a separate data-file generated by the random sequence constructor.

For evaluation of included calls and adherence to protocol all randomized, EMS treated OHCA dispatch calls will be audited. All audit evaluators will be blinded to allocation. A standardized template for evaluation of dispatcher assisted CPR will be used (cardiac arrest registry to enhance survival – CARES).(25) The study specific inclusion criteria will be added as auxiliary variables (supplementary app).

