## 10.4 Analysis step and strategy of the whole study populations

The target study population is witnessed OHCA of medical origin where any bystander at the scene has previous CPR training. All randomized calls of suspected OHCA will be included.

Patient with previous decision that CPR should not be initiated i.e. terminal illness or palliative care and cases where EMS did not start CPR for other reasons (sure signs of death, not true OHCA) will be excluded from data analysis. The remaining patients will be analyzed in the ITT population.

Blinded call audit will be used to define type of CPR instructions provided. All randomized EMS treated OHCA receiving instructions in accordance with randomized allocation will be treated as the target study population treated per protocol (PP1).

Finally, patients who are randomized but later judged as not fulfilling all criteria for inclusion before randomization, as evaluated by call audit (not witnessed, asphyxic, bystanders with no previous CPR training), will be removed and remaining patients will be analyzed as PP2.

Thus, we perform ITT analysis, PP1 and PP2 analysis based on the following patients:

Intention to treat (ITT) analysis: We define the ITT population as all included and randomized EMS treated OHCA patients that not fulfilled any exclusion criteria's.

Per protocol 1 (PP1): We define the PP population as the subset of the ITT population where the bystanders received the allocated instructions by the dispatch operator, as defined by the call audit.

Per protocol 2 (PP2): We define the PP2 population as the subset of the PP1 population where the patients fulfilled all inclusion criteria, as defined by call audit.

Please see also Consort Diagram in section 10.5.

The reasoning behind excluding patients after randomization is two-folded:

First: Dispatchers suspecting OHCA based on initial information in a phone-call do patient inclusion and randomization. In this situation there is very limited information and dispatchers are encouraged to treat all calls where the patients are not conscious and not breathing normally as suspected OHCA

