## 10.5 Power and sample size estimation

We estimated that 3260 patients (1630 in each group) would be needed in the primary analysis PP1 to have 80% power to show that CO-CPR is non-inferior to standard CPR. This calculation is based on the assumptions that the true survival rates after 30 days (primary outcome) in the population for standard CPR is 11% compared with 13.1% for CO-CPR, and that alpha (1 tailed) is set at 2.5%.

We defined 1.0 percentage point or less as the largest difference in survival that is clinically acceptable (i.e. the non-inferiority level which imply that a difference bigger than this would matter in practise). This difference is equivalent to an NNT of 100 (one person of 100 will die among those recommended CO-CPR, due to this recommendation). The reason for accepting this difference relies on the assumption that CO-CPR is easier to teach and perform, and therefore the treatment can be offered to more victims (please see also section 9.3).

In addition, we assumed that 20% will not receive the allocated intervention (e.g. randomized to CO-CPR but received S-CPR instructions or vice versa). We also assumed that 40% of the included patients will be excluded because of exclusion criteria's not possible to detect at the randomization (not OHCA, see section 5.3). Therefore, the recruitment goal was set to 6792 ( $3260 / (0.8 * 0.6)$ ) randomized cases of suspected out-of-hospital cardiac arrest in order to receive 3260 in the primary PP1 analysis. (Please see also Consort Flow Diagram below)

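### Section 11 gives 3260 as the number enrolled, but section 10.5 makes 3260 the PP1 analysis count and sets recruitment at 6792 randomised cases

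*Combined protocol and SAP*

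**What the plan says.** Section 10.5 derives the sample size: "We estimated that 3260 patients (1630 in each group) would be needed in the primary analysis PP1". It then allows for two losses between randomisation and PP1. For the first, "we assumed that 20% will not receive the allocated intervention". For the second, "We also assumed that 40% of the included patients will be excluded" because of conditions that cannot be detected at randomisation. It concludes: "Therefore, the recruitment goal was set to 6792", described as "randomized cases of suspected out-of-hospital cardiac arrest in order to receive 3260 in the primary PP1 analysis". Each number in section 10.5 has its unit.

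Section 11, on the monitoring committee, says that the committee may declare a sufficient difference in the primary outcome or "recommend that the study is continued until 3260 patients have been enrolled". That sentence mentions neither PP1 nor 6792. The same section sets interim looks at 750 and 1500 patients. It also reports a review in early 2022 after 1250 patients, of whom 696 were in PP1.

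Section 10.4 defines the populations: "We define the ITT population as all included and randomized EMS treated OHCA patients" with no exclusion criterion met. PP1 is the part of that population in which the bystander was given the allocated instruction, as judged by call audit.

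**The concern.** The same number stands for two different counts. Section 5 ties enrolment to meeting the eligibility criteria, and section 6.2.1 has the dispatcher apply those criteria before randomisation. The exclusions in section 5.3 come after randomisation, and PP1 status comes later still, from the audit. A PP1 count is therefore not a count of patients enrolled in the document's own sense. Section 11 does use the PP1 label, for the 696, but not for the 3260.

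Section 11 is the text that tells the committee how long the trial is to run, so it should carry the right number with the right unit. A committee that took 3260 as randomised cases would end the trial at less than half of its recruitment goal. Correcting the phrase also settles which count ends recruitment. The two counts in section 10.5 coincide only if 48% of randomised cases reach PP1.

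**Working it through.** **Inputs.** From section 10.5: 3260 in PP1 (1630 per group), 20% not receiving the allocated instruction, 40% excluded after randomisation, 30-day survival 11% (S-CPR) and 13.1% (CO-CPR), margin 1.0 percentage point, one-sided alpha 2.5%, stated power 80%. From section 11: 3260 enrolled, and 696 of 1250 in PP1.

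**Step 1: the plan's recruitment goal.** Planned yield = 0.8 × 0.6 = 0.48. Then 3260 / 0.48 = 6791.7, rounded up to 6792. The stated figure is reproduced. Ratio of the two counts: 6792 / 3260 = 2.08.

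**Step 2: power formula.** With a normal approximation and unpooled variance,

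power = Φ(0.031 / √(v / n) − 1.96),

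where n is the number per group, 0.031 = 0.131 − 0.11 + 0.01, and v = 0.11 × 0.89 + 0.131 × 0.869 = 0.211739.

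**Step 3: baseline at 3260 in PP1.** With n = 1630, √(0.211739 / 1630) = 0.01140. Then 0.031 / 0.01140 − 1.96 = 0.76, and power = 77.6%. This formula gives a little less than the stated 80%, so any loss should be measured from about 78%.

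**Step 4: section 11 taken literally.**

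| Meaning of 3260 in section 11 | In PP1 at planned rates | n per group | Power |
|---|---|---|---|
| In PP1 (as in section 10.5) | 3260 | 1630 | 77.6% |
| EMS-treated cases | 3260 × 0.8 = 2608 | 1304 | 68.2% |
| Randomised cases | 3260 × 0.48 = 1564.8 | 782.4 | 47.0% |

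**Step 5: does it matter which count ends recruitment?** 696 / 1250 = 55.7%. Section 11 does not say what the 1250 are.

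- If they are randomised cases, the comparison is with the planned 48%. The 95% interval is 0.5568 ± 1.96 × √(0.5568 × 0.4432 / 1250), or 52.9% to 58.4%, which excludes 48%. At this yield, 3260 in PP1 is reached at 3260 / 0.5568 = about 5855 randomised, while 6792 randomised gives 6792 × 0.5568 = about 3782 in PP1. The two possible end points are 6792 − 5855 = 937 randomised cases apart.
- If they are EMS-treated cases, the comparison is with the planned 80% receiving the allocated instruction, and 55.7% falls well short of it.

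On either reading the reported figures depart from plan, so the two counts in section 10.5 cannot be assumed to coincide.

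**The case against.** The strongest reply is that nobody would be misled. Section 10.5 states both numbers with their units and says that 6792 exists to yield 3260 in PP1. It is also the only place where 3260 is derived, so section 11 very probably means 3260 in PP1. That stands, and it is why the 47% and 68% figures describe a consequence of literal reading and not an expected result. It does not make the sentence correct: the intended meaning has to be inferred from another section. Section 10.5 also refers the reader to a CONSORT diagram that is not shown, so a clarification there cannot be ruled out.

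A second reply is that a recruitment target need not come with a rule for every departure from the assumed losses. That is fair. Taken alone, the missing rule is absent detail and not a contradiction. It needs no separate addition, because a corrected phrase in section 11 will state which count governs.

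Three stronger readings are tempting and are not supported.

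- A reader might infer that the trial is really planned at 3260 randomised and is badly underpowered. The explicit goal of 6792 speaks against this.
- A reader might treat the 1250 as EMS-treated, multiply 55.7% by the planned 60% share, and conclude that the trial will fall far short in PP1 at 6792 randomised. Section 11 does not label the 1250, and the documents give no observed EMS-treated share to multiply by.
- A reader might see a type I error problem in the unnamed population for the 750 and 1500 looks. Early stopping for efficacy requires p of 0.001 or less. The committee may also analyse at any time, so a bound worked out for a fixed number of looks would mean little. Naming that population is a minor clarification.

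**Conclusion.** The concern holds as a wording error that should be corrected. Section 11 attaches 3260 to enrolment, section 10.5 attaches it to PP1 with 6792 randomised, and the two differ by a factor of 2.08. No available text reconciles them.

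The power figures (about 47% if randomised, about 68% if EMS-treated, against about 78% by the same formula) rest on the survival rates and losses assumed in section 10.5. They apply only if section 11 were followed over section 10.5, which is unlikely. The practical part is the choice of count. The sponsor already holds the numbers that show what the 1250 are, and the end of recruitment could move by about 937 randomised cases if they are randomised cases and the 55.7% yield persists. The sample size calculation, population definitions and analysis are not affected.

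**What to change.** The sponsor should confirm its intent and replace the phrase in section 11 with one of the following:

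- *until 6792 cases have been randomised (planned to give 3260 in PP1, section 10.5)*; or
- *until 3260 patients are in the PP1 population (planned 6792 randomised, section 10.5)*.

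Either wording removes the contradiction and states which count ends recruitment. In the same edit, section 11 can name the population for the 750 and 1500 looks and say whether the 1250 are randomised or EMS-treated cases.

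The cost is a few sentences, using counts that the sponsor already has. With the first option nothing operational changes, but the final PP1 number will vary with the yield. With the second, the blinded call audit must be kept current during recruitment, because PP1 membership depends on it. Section 8 already provides that "all randomized, EMS treated OHCA dispatch calls will be audited", so the added demand is timeliness and not extra auditing.

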## 12. Publication plan and author policy

The trial will be analyzed by an independent statistician and the results interpreted by the steering group. The principal investigator will prepare the manuscript before the allocation code is broken. The final manuscript will be submitted to a peer-reviewed international journal. Authorship will be granted using the Vancouver definitions and depending on personal involvement. The author list will start with [name] and the last name will be [name]. A separate publication list for all authors including the main study, as well as sub studies, has been created.

## 13. Enrolment and timeline

Q1-2 2014	Application to ethics committee
Q3-4 2014	Preparation
2015-2016	RUN-IN study
2017-2020	PILOT study
2022-2026	MAIN STUDY

